### **Aim 3: Patient-Level Predictors of Effectiveness:**

Baseline and longitudinal predictors of interest in naltrexone alcohol treatment efficacy and effectiveness trials include gender, ethnicity, mu opioid receptor genotype, and ancillary alcohol behavioral treatment involvement. Naltrexone's relative ineffectiveness in African American clinical trial sub-populations, including in the COMBINE trial, is possibly mediated by low rates of the Asp40 OPRM1 functional allele in persons of African descent, who are primarily Asn40 homozygous. This Asp40 (A118G, 'G' allele) OPRM1 functional single nucleotide polymorphism has been shown to be associated with successful treatment with naltrexone. A pilot conducted by [name] at Bellevue did find a strong association between persons involved at baseline or who became involved during primary care XR-NTX treatment with specialty alcohol treatment and/or Alcoholics Anonymous. Thus, we hypothesize a priori that there will be less robust effectiveness among African Americans; voluntary specialty alcohol treatment and Alcoholics Anonymous involvement, and presence of the Asp40 OPRM1 SNP will be associated with treatment effectiveness. We note, however, that these analyses will be exploratory, as the study is not powered to carefully test these secondary hypotheses.

We will collect patient-level characteristics data to explore the association of patient-level characteristics (e.g. sex, race) with effectiveness. We will be able to carefully track prior detox admissions and concurrent 12-step and specialty alcohol treatment involvement in the proposed trial in order to estimate associations with treatment effectiveness. Multivariate models will be used to identify patient characteristics associated with treatment success. The analysis will utilize a logistic regression with an indicator variable for treatment and covariate terms for baseline potential prognostic indicators, including African American ethnicity, baseline drinking severity, and status of housing, social support, quality of life, and OPRM1 genotype. Odds ratios will be calculated to quantify the risk to treatment failure of significant predictors. As originally proposed, naltrexone appears most effective at reducing heavy drinking, as opposed to producing complete abstinence. A harm reductionist perspective delineating treatment success from failure is particularly important in this population having a greater severity of AUD and psychosocial dysfunction. All traditional alcohol treatment trial clinical endpoints, including continuous

CONFIDENTIAL

This material is the property of the NYU School of Medicine and Langone Medical Center. Do not disclose or use except as authorized in writing by the study sponsor

drinking and heavy drinking variables, as well as the %CDT biomarker, the change in CDT, and the combined CDT-GGT equation, which are specific for heavy drinking, are of great interest, and will be reported.

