**Aim #3: To identify patient-level characteristics associated with effectiveness.**

Hypothesis: Exploratory analysis of patient and system-level characteristics possibly associated with effectiveness will inform treatment choice to maximize the probability of successful outcome. Factors assessed will include data collected in ongoing investigations of pharmacotherapy for alcohol dependence, including mu opioid receptor (OPRM1) genotypes, to facilitate comparison across study populations and settings.

XR-NTX+CM is a potentially powerful treatment for this population that suffers poor health and psychosocial outcomes and has a disproportionate impact on public resource utilization. We will identify methods to enhance the feasibility and acceptability of its implementation in the ED as well as to ensure that future study can be carried out efficiently and rigorously. We anticipate using this data to support a future R01 application to test the intervention's effectiveness as well as other health services research that uses the ED to extend the reach of AUD treatment. This data is essential to influence policy and practices regarding evidence-based treatment for AUDs and to ensure this necessary care is provided in an integrated health system, particularly for those who only present to EDs under gravely compromised circumstances.

CONFIDENTIAL

This material is the property of the NYU School of Medicine and Langone Medical Center. Do not disclose or use except as authorized in writing by the study sponsor

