### 3.3 Secondary Study Endpoints

To conduct an exploratory analysis of the effect of this intervention on healthcare utilization and engagement, drinking outcomes, and quality of life. We will also explore patient-level predictors of effectiveness.

We will explore the relative efficacy of XR-NTX+CM to standard care on decreasing acute healthcare use (ED, inpatient, Emergency Medical Services), associated expenditures, and cost-effectiveness. Secondarily, we will explore effects on healthcare engagement (clinic use, medication adherence, motivation to change), alcohol quantity/frequency, alcohol-related problems, and quality of life measures.

CONFIDENTIAL

This material is the property of the NYU School of Medicine and Langone Medical Center. Do not disclose or use except as authorized in writing by the study sponsor

See Attachment #2. We will evaluate and compare the performance of CDT and the combination of CDT-GGT as an objective measure of alcohol consumption and its correlation to self-report. We will also conduct an exploratory analysis of patient and system characteristics possibly associated with effectiveness. These data will be used to inform the individualization of treatment choice to maximize the probability of successful outcome. Factors assessed will include data collected in ongoing investigations of pharmacotherapy for alcohol dependence to facilitate comparison across study populations and settings. This specifically includes the analyses modeled on those performed in an ongoing study directed by [name] (R01AA020836; S12-02263) at NYU. All data analyzed will be de-identified and linked by a unique identification number.

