**Intervention Arm:**

1. PI will administer XR-NTX 380mg as an intramuscular gluteal injection (after urine drug screen is confirmed to be negative for opioids).
2. PI/RA will facilitate a harm-reduction based motivational interview and psychosocial assessment with the social worker or care manager (if available) that focuses on harm reduction and identification of subjects' goals and needs to inform ongoing care management plan. PI will train future staff. See therapy manual - Attachment #3. Subjects' healthcare, housing, and social assistance will be coordinated through the CM model.
3. Notify homeless services outreach of subject if homeless. Subject will be assigned a homeless outreach case worker and be offered shelter if eligible.
4. Provide referral to Bellevue Chemical Dependency clinic (or a suitable alternative) for ongoing alcohol-medical management. Subjects will be navigated directly to the clinic on their enrollment visit if possible. Subjects will receive a one-week referral to Bellevue ambulatory care for initial Alcohol-Medical Management (MM) and will also be scheduled every 4 weeks (or after most recent XR-NTX injection) for MM and XR-NTX injections (for a total of up to 12 injections).
5. Provide card containing the PI's contact information, dates of XR-NTX administration, and relevant medication information for medical personnel.

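### Aim 3 uses AA and specialty-treatment involvement arising after randomisation as a predictor of effectiveness, so its association with success cannot be interpreted or used to guide treatment choice

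*Combined protocol and SAP*

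**What the plan says.** Section 7.2.2, Aim 3, opens with "Baseline and longitudinal predictors of interest in naltrexone alcohol treatment efficacy and effectiveness trials include gender, ethnicity, mu opioid receptor genotype" and ends that list with involvement in ancillary behavioural treatment. It cites a primary-care pilot that found a strong association for "persons involved at baseline or who became involved during primary care XR-NTX treatment", which merges involvement before and after treatment start. From this it derives an a priori hypothesis that "voluntary specialty alcohol treatment and Alcoholics Anonymous involvement, and presence of the Asp40 OPRM1 SNP will be associated with treatment effectiveness". The next paragraph says the trial will track prior detoxification admissions and "concurrent 12-step and specialty alcohol treatment involvement in the proposed trial in order to estimate associations with treatment effectiveness".

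The intended use is stated twice. Section 2, Aim #3, says the exploratory analysis of patient and system characteristics "will inform treatment choice to maximize the probability of successful outcome". Section 3.3 says: "These data will be used to inform the individualization of treatment choice to maximize the probability of successful outcome".

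Aim 3 also describes one regression: a logistic model for treatment success with a treatment indicator and baseline prognostic covariates. In-trial involvement is not among the covariates named. The same section calls the Aim 3 analyses exploratory and says the study is not powered for them.

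**The concern.** A predictor meant to guide treatment choice has to be known when treatment is chosen. AA attendance or specialty care that starts during follow-up is not. It is also partly a product of things that happen after randomisation, and the protocol supplies several of them:

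- **Arm.** For the intervention arm, Section 6.1 lists "Provide referral to Bellevue Chemical Dependency clinic (or a suitable alternative) for ongoing alcohol-medical management", with direct navigation to the clinic where possible, care management and four-weekly scheduling. Section 3.1 gives the standard care arm a referral at enrolment and another offer at study close.
- **Poor drinking course.** Section 1.6.1 says subjects in either arm who cannot stop drinking, or who suffer severe consequences, are encouraged at any point towards detoxification and specialty treatment.
- **Withdrawal.** Section 4.4.1 refers all withdrawn subjects for further addiction treatment.
- **Early success.** Someone who cuts down and stays in contact may be more likely to attend. The documents do not say this, but nothing in the plan rules it out.

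The protocol's own causal picture points the same way. The Figure 3 caption treats engagement, including clinic participation, as a possible mediator, and Aim 2b lists healthcare engagement as an outcome. Aim 3 then uses a closely related variable as a predictor. At stake is an association, set up as a prespecified hypothesis, that could be reported as a guide to treatment when it reflects who was doing well, who was doing badly, or who was navigated to a clinic.

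**Working it through.** **Timing.** The plan's words cover involvement at baseline and during the trial. No section restricts the hypothesis to baseline, sets a landmark time, names a time-varying or mediation method, or defines the word voluntary in a way that would separate self-initiated from protocol-prompted attendance. The concurrent-involvement analysis therefore has a hypothesis and a purpose but no specified model.

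**Inputs.** The documents give no involvement rate, success rate or power figure for Aim 3, so there is no stated figure to reproduce. All rates below are assumptions. In steps 1 and 2 involvement has no effect on success.

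**1. Success or failure drives involvement.** Let a be the proportion involved among successes and b the proportion among failures, the same in both arms. The odds ratio within each arm, and so also after adjusting for arm, is [a/(1−a)] / [b/(1−b)].

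| Successes involved (a) | Failures involved (b) | Odds ratio |
|---|---|---|
| 30% | 20% | (0.30/0.70)/(0.20/0.80) = 1.71 |
| 40% | 20% | (0.40/0.60)/(0.20/0.80) = 2.67 |
| 50% | 20% | (0.50/0.50)/(0.20/0.80) = 4.00 |
| 20% | 40% | (0.20/0.80)/(0.40/0.60) = 0.38 |

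The last row is the pattern to expect if subjects doing badly are the ones directed to specialty treatment.

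In simulated trials with success 40% versus 30% by arm and the second row's involvement rates, a logistic model with arm and involvement gave p < 0.05 for involvement in about 29% of trials at N = 50 and about 95% at N = 300. More subjects make the artefact more significant.

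**2. Arm drives involvement.** Assume success 50% versus 30% by arm and equal arm sizes.

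- Involvement 30% versus 20%: the cell sums over the two arms are 0.21 (involved, success), 0.29 (involved, failure), 0.59 (not involved, success) and 0.91 (not involved, failure). The crude odds ratio is (0.21 × 0.91)/(0.29 × 0.59) = 1.12.
- Involvement 50% versus 20%: (0.31 × 0.81)/(0.39 × 0.49) = 1.31.

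Both return to 1.0 once arm is in the model. Arm alone is thus a small and removable source; the within-arm sources in step 1 are neither.

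**3. Involvement carries the arm effect.** Here involvement does act: success is 60% if involved and 30% if not.

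- Involvement 40% versus 20%: success is 0.4 × 0.6 + 0.6 × 0.3 = 42% versus 0.2 × 0.6 + 0.8 × 0.3 = 36%. The arm odds ratio is (0.42/0.58)/(0.36/0.64) = 1.29.
- Involvement 50% versus 20%: success is 45% versus 36%. The arm odds ratio is (0.45/0.55)/(0.36/0.64) = 1.45.

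Conditioning on involvement takes both to 1.0. This matters only if involvement is put into the model that estimates the arm effect.

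**The case against.** The strongest reply is that the plan promises little. It speaks of associations, calls Aim 3 exploratory and says it is not powered. The one model it describes uses baseline covariates and an arm term. The treatment-choice statements concern patient and system characteristics in general and do not name AA or specialty care. The four-weekly visits and the cited clinic referral are for medical management, whereas the hypothesis concerns voluntary specialty treatment and AA. Specialty services are open to both arms, and engagement is already an Aim 2b outcome.

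Much of this stands, and it rules out three stronger readings.

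- A reader might infer that the planned regression adjusts for in-trial involvement and so removes part of the randomised effect. The covariates are described as baseline ones and involvement is not listed. Step 3 applies only if it were added.
- A reader might infer that the hypothesis is bound to be confirmed. It is not: referral of subjects who are doing badly or withdrawing pushes the association the other way.
- A reader might infer that the difference in referral between arms is the main problem. Controls are referred too, and again offered a referral at study close, and step 2 shows that adjusting for arm removes that component.

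What does not stand is the exploratory label as a cure. It warns about precision, not bias. The hypothesis about involvement is stated in advance, its supporting pilot mixes baseline and later involvement, and nothing excludes that analysis from what Aim 3 is meant to inform.

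**Conclusion.** The point holds for the separate analysis and hypothesis relating in-trial involvement to effectiveness. Followed as written, it would give an association that could be well above or well below 1 with no true effect: 1.7 to 4.0, or 0.38, under the assumed rates. These figures show what is possible; they are not estimates for this trial, because the documents contain no involvement rates. Whatever its value, the association could not guide treatment choice, since the variable does not exist when the choice is made.

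The weight is moderate. Aim 3 is secondary, exploratory and unpowered, and the randomised comparison is unaffected by the plan as it stands. The correction is still worth making, because the bias does not shrink with sample size.

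**What to change.** In Section 7.2.2, Aim 3:

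1. Restrict predictors to values known at randomisation. Test the AA and specialty-treatment hypothesis with involvement and prior detoxification recorded at week 0.
2. State that in-trial involvement will not enter the logistic regression and is outside the treatment-choice statements in Sections 2 and 3.3.
3. Report in-trial involvement by arm as an engagement outcome alongside Aim 2b. Label any tabulated association with success as descriptive and non-causal.

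The cost is SAP wording. Form 90 is given at enrolment and follow-up (Sections 6.1 and 7.2.1) and is described as covering medical and self-help services. Because only selected questions from the instruments are used, confirm that those items are kept at week 0. What is given up is the exploratory use of in-trial involvement as a predictor. No sample-size figure changes.

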## 3 Study Design

### 3.1 General Design

This a phase IV, randomized, open-label, non-placebo-controlled, single-center study of the feasibility, acceptability, and effect of initiating treatment in the ED with extended-release naltrexone 380mg intramuscular injection compared to standard care in subjects with severe alcohol use disorders (i.e. alcohol dependence) and frequent emergency department use. In the first two years, we will finalize study preparations, recruit and randomize 50 subjects for the pilot phase of this study. The duration of each subject's participation will be 12 months. Thereafter, in the second phase of study, we will enroll an additional 250 subjects (for a total of 300 subjects) to address remaining feasibility and acceptability concerns and test effects.

The study investigators (PI and RA) will collect process data, including barriers and facilitators encountered in the completion of all study procedures. For the following study procedures, study investigators (the PI and RAs) will enter data directly into NYUMC-internal REDCap system for use on portable tablet computers. NYUMC internal REDCap is HIPAA compliant and data will be stored on secure servers with access only to authorized study personnel.

**Brief Synopsis of Study Procedures: The following study procedures are described in greater detail elsewhere in this protocol.**

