## 7 Statistical Plan

### 7.1 Sample Size Determination

Naltrexone has not demonstrated a robust treatment effect; however, most studies did not use the XR-preparation, are limited by poor adherence, and did not include this higher-severity population or other intervention components. We do not know what the “ideal” population for XR-NTX is, but posit that it may have a greater effect size in this more severely affected population than amongst the higher socioeconomic status population historically targeted. A recent pilot of XR-NTX suggests a possible greater effect (and acceptability) in a population similar to ours. Our literature search yielded no studies of initiating pharmacotherapy for alcohol dependence in the ED. There are only limited data on XR-NTX effects on several long-term outcomes of interest, including healthcare use, treatment engagement, and quality of life measures. ED-based case management studies demonstrate promising healthcare utilization outcomes, but most were uncontrolled and overestimated effect because of regression to the mean. The heterogeneity in study designs, interventions, and cohort characteristics precludes meta-analysis.

Determining sample size is challenged by limitations in the existing data and heterogeneity of populations. Definitively testing the relative effects of intervention components may require additional arms with as many as 75 to 200 subjects in each. Thus, we chose to start with the strongest intervention and compare it to standard care to maximize the likelihood of seeing an effect and of exploring effect size on various outcomes. The 2-arm design will minimize the loss of power and allow us to focus on the primary goal of assessing feasibility.

The first phase of study will be a feasibility and acceptability study, through which we will obtain preliminary data to inform the power analysis for the subsequent definitive trial. In the first phase, we plan to pilot the study in 50 subjects. In the second phase of study, we project enrolling 125 subjects in each of the two arms to definitively test the intervention’s effect on multiple outcomes of interest. Thus, we

CONFIDENTIAL

This material is the property of the NYU School of Medicine and Langone Medical Center. Do not disclose or use except as authorized in writing by the study sponsor

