project enrolling a total of 300 subjects in both phases. These estimates are founded in the current literature and the analyses, hypotheses, and predictions of experts in the field.

[name]'s ongoing study (R01AA020836) comparing the effectiveness of oral naltrexone to XR-NTX in alcohol dependent primary care patients has a targeted enrollment of n=117 in each of the two arms to detect a 20% absolute difference in primary clinical outcomes based in the Fisher's exact test with a projected power of 90%. [name], PhDs' (R01 AA022309) four-arm RCT of alcohol dependent homeless individuals recruited from a community housing program (XR-NTX + Counseling, Placebo + Counseling, Counseling alone, Treatment as Usual) will enroll a total of 300 patients (N=75/arm). This study population is similar to the one we will be studying.

A sample of 125 subjects per arm would allow us to detect a moderate effect size (Cohen's d of slightly less than 0.40) to provide power of 0.80 or greater at  $\alpha < .05$ . Another consideration when determining sample size is to power the study to detect the reduction in ED visits that would entirely offset the cost of medication. The institutional costs of a dose of Vivitrol (XR-NTX) is comparable to the estimated institutional cost of a single ED visit to Bellevue Hospital (according to the New York State Institute Cost Review). To detect a difference of  $\geq 6$  ED visits (i.e. a 6 month course of Vivitrol) between study arms comprised of subjects having a mean of  $22 \pm 15$  ED visits per year (per our pilot study data), would require 100 subjects per arm with  $\alpha = 0.05$ ;  $\beta = 0.20$  or, more conservatively, 133 subjects per arm with  $\alpha = 0.05$  and  $\beta = 0.10$ .

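### Aim 3's logistic model has at least seven terms and no stated data set; if fitted on the 50 phase 1 subjects by ordinary maximum likelihood, non-null log odds ratios would be inflated by about 20–30% on average

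*Combined protocol and SAP*

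**What the plan says.** The Aim 3 part of Section 7.2.2 sets out the model: "The analysis will utilize a logistic regression with an indicator variable for treatment and covariate terms for baseline potential prognostic indicators". The covariates named are "African American ethnicity, baseline drinking severity, and status of housing, social support, quality of life, and OPRM1 genotype". The word that introduces this list leaves it open, so other covariates may be added. Odds ratios are then to be calculated for predictors found significant. The section mentions no penalisation, shrinkage, exact method or limit on the number of terms.

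The outcome is treatment success against failure. The nearest the section comes to a definition is "A harm reductionist perspective delineating treatment success from failure is particularly important in this population". No rule for success and no expected success rate are given.

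On size, Section 7.1 says "In the first phase, we plan to pilot the study in 50 subjects", and for the study as a whole that the team "project enrolling a total of 300 subjects in both phases". Aim 3 is assigned to neither. Section 7.3 says only that the analysis population is everyone randomised. The Aim 3 text does say that these analyses are exploratory and that the study is not powered for them.

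**The concern.** Maximum likelihood estimates of log odds ratios are biased away from zero in small samples, and the bias grows as the number of subjects in the smaller outcome group, per model term, falls. Seven terms on 50 subjects is in the range where this shows. A sparse factor, such as a genotype carried by a minority, can also separate the outcome, and the fit then has no finite estimate.

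Section 2 says that the patient-level analysis will inform treatment choice, and Section 3.3 repeats this. Odds ratios for patient characteristics that sit systematically too far from 1 would overstate how well those characteristics distinguish patients. The exploratory, unpowered label prepares a reader for wide intervals, but not for estimates that are shifted on average. Nor does the bias depend on the plan's focus on significant predictors: it is present when every coefficient is reported. Selecting on significance would add a separate inflation that is not counted here.

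**Working it through.** The plan gives no sample size, event count or power for Aim 3, so it has no figure of its own to reproduce.

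**Inputs from the documents**
- Phase 1: 50 subjects; both phases: 300 (Section 7.1).
- Allocation 1:1: stated for phase 2 ("we project enrolling 125 subjects in each of the two arms"), and consistent with the block sizes of 2, 4 and 6 used throughout.
- Terms: treatment + 6 named covariates = 7, not counting the intercept. This is a minimum.
- African American share: 40%, the figure for Bellevue patients in Section 4.3.6.

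**Assumptions**
- Success rate 40–50%, varied from 10% to 70%.
- Unassessed subjects: missed visits are expected (Section 6) but no rate is given, so N = 40, 35 and 30 were also run.
- True treatment odds ratio (OR) of 2, with 0.5, 1.5 and 3 also tried; covariate effects and the prevalence of the binary covariates.

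**Successes per term at N = 50**
- 40% success: 0.40 × 50 = 20, and 20 / 7 = 2.9.
- 50% success: 0.50 × 50 = 25, and 25 / 7 = 3.6.

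**Simulation.** Logistic data were generated with treatment and six covariates, some binary and some continuous, and fitted by ordinary maximum likelihood (ML) and by Firth's method, with 1,500 to 6,000 data sets per scenario. Relative bias = mean(estimated log OR) / true log OR − 1. ML fits that separated or did not converge were left out of the mean and counted separately.

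| Scenario | ML bias, treatment log OR | ML fits lost |
|---|---|---|
| N = 50, 40–50% success | +20% to +31% | about 1–4% |
| N = 50, 30% success | +31% | 3.5% |
| N = 50, 20% success | +36% to +37% | 14–15% |
| N = 50, 60% success | +27% | 3% |
| N = 50, 70% success | +30% | 10% |
| N = 40, 50% success | +28% to +38% | 3–6% |
| N = 35, 45% success | +40% | 7% |
| N = 30, 45% success | +50% | 13% |
| N = 50, 45% success, 10 terms | +37% | 1% |
| N = 300, 45% success | +3% | 0% |

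- The central case (N = 50, 45% success, OR 2) gives +26%, Monte Carlo standard error 2 points. The median is lower (+20%), because the estimates are skewed. Across 40–50% success the medians run from about +16% to +24%.
- With non-null covariates, the average covariate log OR is inflated by +24% to +30%.
- With every binary covariate split evenly, no fit was lost at N = 50, so separation depends on sparse factors.
- At 10% success, 57% of fits fail and the mean of the rest has little meaning.

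**On the odds ratio scale.** An inflation factor k turns a true OR into OR^k.
- 2^1.2 = 2.30 and 2^1.3 = 2.46.
- 3^1.2 = 3.74 and 3^1.3 = 4.17.
- 0.5^1.27 = 0.41.
- 1^k = 1, so a null effect is not shifted.

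**Firth on the same data.** At N = 50 and 20–70% success, treatment bias is −3% to +6% and average covariate bias 0% to +4%. Two further sets of runs, with other assumed covariate effects, gave ML means of 1.29 and 1.27 times the truth at N = 50. Root mean squared error (RMSE) fell from 0.84 to 0.67 and from 0.96 to 0.72 with Firth, reductions of 20% and 25%. At N = 40 the ML means were 1.34 and 1.40 times the truth, and RMSE fell from 1.07 to 0.81 and from 1.23 to 0.81. At N = 300, ML was within about 4%.

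**The case against.** **The model may never be fitted on 50 subjects.** This stands as a limit on the point. No section assigns Aim 3 to phase 1. Where the authors mean phase 1 they say so, as in the Aim 2c biomarker substudy. Section 15.1 also shows that money for the genomic analyses was still to be sought, so the genotype term might be unavailable in phase 1. But nothing rules out a phase 1 fit, and two things make it plausible: the same section says that the award finances the initial phase and that phase 2 funding was still to be sought, and Section 2 expects the data to support a further application. Dropping genotype leaves six terms, and ML is then still 1.19 times the truth at N = 50 and 1.30 times at N = 40.

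**The bias is small beside the noise.** This is true. With a bias of 29%, 0.29 × ln 2 = 0.20, against an RMSE of 0.84; squared bias is 0.04 / 0.71, or about 6% of mean squared error. With a standard error of 0.8, the 95% interval around an OR of 2 is exp(0.69 ± 1.96 × 0.8), about 0.4 to 9.6. Imprecision is the larger problem, and the plan admits it. Firth's method still helps, because it lowers the RMSE as well as the bias.

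**A reader might infer that an inflated treatment odds ratio would mislead the sizing of phase 2.** The documents do not support that. In Section 2 the effect-size input to phase 2 belongs to Aim 2, which Section 7.2.2 analyses by changes in scores, paired tests and difference-in-differences regression. The Aim 3 odds ratio is not named as an input. What it bears on is the patient characteristics meant to guide treatment choice.

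**Conclusion.** The point holds conditionally and is minor. If the seven-term model is fitted on phase 1 by ordinary maximum likelihood, with an assumed 40–50% success rate, non-null log odds ratios are inflated by about 20–30% on average and about 1–4% of fits separate. At 20–30% success, or with a fifth of subjects unassessed, the inflation is roughly 30–40%; at 20% success, separation reaches 14–15%. On the pooled 300 the bias is about 2–5% and needs no action.

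The size rests on the assumed success rate, covariate effects and prevalences. The direction does not: every non-null scenario run at N = 50 showed inflation away from 1. The documents do not support saying that the plan will fit this model to 20–25 successes, since they give no phase, no definition of success and no rate. What they support is that the data set is unstated, that a phase 1 fit is open, and that the caveat about power does not cover the bias such a fit would carry.

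**What to change.** In the Aim 3 part of Section 7.2.2, state which data set the logistic model is fitted on. Then choose one of two rules:

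- For any fit on phase 1 data, use Firth's penalised likelihood with profile penalised-likelihood confidence intervals.
- Or fit the full model only on the pooled 300 and report the phase 1 predictors descriptively.

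Firth's method is not needed on the pooled data. Either rule presupposes a definition of treatment success, which the section still has to supply.

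The cost is a line of SAP wording and a standard software option. The downside is slightly smaller phase 1 odds ratios. Design, sample size and clinical conduct are unaffected.
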